### 9.8. Pregnancy

Pregnancy results from serum or urine pregnancy testing will be listed for all participants.

### 9.9. Vital Signs and Pulse Oximetry

Systolic and diastolic blood pressure, heart rate, respiratory rate, oxygen saturation, temperature, height, weight, and BMI will be collected at protocol specified visits.

Descriptive summaries of actual values and changes from baseline will be based on available data and will be provided by visit and treatment group.

Arithmetic mean plots of vital signs and oximetry parameters over time will be prepared. The standard deviation will be included at each sampled time point.

### 9.10. Electrocardiogram

ECG parameters will be collected at protocol specific visits.

Descriptive summaries of actual values and changes from baseline will be based on available data and will be provided by visit. Investigator and central reading interpretation will be summarized by visit, too.

A categorical summary of QTcF interval will be provided using counts and percentages at baseline and maximum post-baseline by treatment for the following categories:

- Result >450 and  $\leq 480$  msec;
- Result >480 and <500 msec;
- Result >500 msec;
- Change from Baseline >30 and ≤60 msec;
- Change from Baseline >60 msec.

Safety 12-lead ECG data will be provided in a data listing.

### 9.11. Physical Examination

Any abnormalities noticed by investigator during the Physical Examination at Screening will be recorded in the medical history, or as an AE if occurred or worsens after ICF.

Dates of Physical Examination will not be listed.

### 9.12. Prior, Concomitant and Post-IP Medications

The ITT Analysis Set (see Section 5.2) will be used for describing medication usage during the study. Classification of used medications into prior, concomitant or post will be done as detailed in Section 6.4.8.

Prior, concomitant and post medications will be summarized separately. The number and percentage of participants reporting the medication will be presented for participants using at least 1 medication, at least one medication at the Anatomical Therapeutic Class Level 4

CONFIDENTIAL Page 80 of 139

(ATC4) level, and by preferred term within ATC4. If ATC Level 4 is not available ATC Level 3 is used instead. If ATC Level 3 is not available ATC Level 2 is used instead.

### 9.13. Prior, Concomitant and Post-IP Procedures

The ITT Analysis Set (see Section 5.2) will be used for describing the number and percentage of participants undergoing a procedure prior to and during study conduct. Classification of procedures into prior, concomitant, or post-treatment will be done as detailed in Section 6.4.8.

Prior and concomitant procedures will be summarized by SOC and PT using the most recent MedDRA version. Participants are counted only once in each SOC and only once in each PT.

Post-treatment procedures will be listed only, while procedures prior to initiation of this study will be listed as part of participants medical history.

### 9.14. Summary of Data After Early Discontinuation of IP

All participants are encouraged to stay in the study regardless of IP discontinuation. Any participants who discontinue from IP will have their reason for discontinuing IP recorded and will continue in the study with their remaining scheduled study visits. The eCRF collection of data does not distinguish visits relative to IP termination milestone, therefore for the purpose of the analysis observations will be flagged if collected after IP early discontinuation. An additional timing variable will be introduced to reflect Study Day relative to EOT for visits occurring beyond treatment discontinuation.

Descriptive summaries will be presented for the subgroup of participants who discontinues IP early based on the available data through the EOS visit. For safety parameters these summaries will present data after 28 days following the last IP intake (>EOT+28 days). The summaries will be limited to the following assessments:

- AE, SAEs and AESIs,
- Laboratory and vital signs assessments.
- Deaths will be listed.

### 9.15. Chest CT Scan for Eligibility

A high-resolution chest CT scan will be performed at the Screening Visit if the participant does not have prior radiological confirmation of NCFBE diagnosis or if the available CT scan was obtained more than 5 years prior to the participants Screening Visit or the existing CT scan cannot be read due to quality issues. Presence of previous scans or date of a new chest CT scan will be listed.

CONFIDENTIAL Page 81 of 139

### 10. PHARMACOKINETIC

The study includes a PK substudy at select sites. The substudy is aimed/designed to include approximately 300 adult participants from whom blood PK will be collected. In addition, blood PK samples will be collected from all adolescent participants and adult participants who enrolled in the main study at selected study visits.

The PK analysis will be based on the Pharmacokinetic Concentration Analysis Set (see Section 5.5) and will include data collected up to the last dose date as steady-state concentrations are of interest. Non-compartmental PK parameters will not be determined in this study.

PK plasma concentrations that are collected outside the acceptable collection windows (see Appendix G) will be flagged in the listing with a footnote that these concentrations are excluded from the concentration summary.

### **10.1.** Brensocatib Plasma Concentration Over Time

### **Concentration Summary Tables:**

Source data as reported from the laboratory will be used for calculation of concentration summary statistics. Concentrations for brensocatib will be summarized by brensocatib dose level, day, and nominal timepoint in three separate tables for PK sub-study, adolescent cohort, and main study. In addition, summary table will be repeated for PK Sub-Study participants who are not under cyclic antibiotics therapy.

For summary tables, the number of BLQs and non-BLQs at each scheduled timepoint will be reported. Summary statistics will be calculated for mean, minimum and maximum only if the number of non-BLQ concentrations at a scheduled timepoint is <3 and other summary statistics will be reported as not calculable (NC). Values BLQ will be set to zero for calculation of descriptive statistics.

The rules followed for calculation and presentation of concentration data with regards to the number of decimal places/significant digits for the listings of participant level concentrations and summary tables of concentration are as follows:

Table 11: Rounding of Plasma Concentration Data in Tables and Listings

Concentration Listings and Tables	Rounding
Individual Concentrations	n s.d. as supplied by bioanalytical laboratory
Minimum and Maximum	n s.d. capped at 4
Mean, SD, Median, GM	n+1 s.d. capped at 4
CV%, gCV%	I d.p.
N, n	whole number

s.d. = significant digits, d.p. = decimal place

#### **Concentration Figures:**

The below displays will be for participants participating the PK/PD substudy, adolescent cohort and main study (for participants with PK concentration data). According to CSP

CONFIDENTIAL Page 82 of 139

Section 8.2 pre-dose blood PK samples will be collected from all participants in the PK/PD substudy and from adolescents for participants on Day 1, Week 4, Week 16, Week 28, Week 40, and Week 52, with an optional 2-hour (±30 minutes) post-dose sample collected at select visits (i.e., Day 1, Week 4, Week 28, and Week 40). For some participants in the main study, PK samples were collected at selected study visits at pre-dose and 2 hours post-dose.

To visualize participant-level concentrations and the comparison between groups for each treatment, the descriptive PK graphs listed below will be generated. LLOQ will be given in a footnote.

- Spaghetti-Plots: Individual participant profiles for plasma concentration data over (actual) time on linear/linear and log/linear scale (log scale for concentration data, time on linear scale) stratified by dose (1 figure per dose level with the individual profiles of the same dose level overlaid) and by groups (PK/PD sub-study, adolescent cohort and main study).
  - o BLQ values on Day 1 pre-dose will be set to 0. When using log/linear scale, these values will be considered missing.
  - o BLQ values will be set to missing except for Day 1 pre-dose.
- Mean (+SD) profiles for plasma concentration data over (nominal) time on linear/linear and log/linear scale by dose level overlaid in the same figure and by groups (PK/PD substudy, adolescent cohort and main study).
  - o BLQ values will be set to 0. When using log/linear scale, these values will be considered missing.

Figures will be generated using unique line style and marker for each plot in the graph. For all PK concentration-time plots, linear scale will be used for the x-axis (i.e., do not use an ordinal scale). Actual sampling time will be used for individual plots while scheduled sampling time will be used for mean plots.

### **Concentration Listings:**

Concentration listings will include nominal PK sampling time, actual sampling times relative to (most recent) dose administration, deviation from nominal time, percent deviation from nominal time, and concentrations. Plasma concentrations below the LLOQ will be presented as BLQ in the listings and the LLOQ value presented as a footnote. There will be 3 separate concentration listings for PK/PD sub-study, adolescent cohort, and main study.

CONFIDENTIAL Page 83 of 139

### 11. PHARMACODYNAMIC

The PK/PD substudy aimed/designed to include approximately 300 evaluable adult participants from whom sputum PD samples will be collected. In a blood PD substudy, NSP blood samples will be collected from approximately 40 of these participants. In addition, sputum PD samples will be collected from all adolescent participants (blood PD samples will not be collected from adolescents). Note, with global protocol amendment 3 (version 6) sputum samples will be collected from all newly enrolled adult participants.

If not stated otherwise, concentration of PD biomarkers (NSP) reported as BLQ will be imputed by LLOQ/2 in all PD data tabulations and plots. LLOQ value will be provided by the laboratory.

The Pharmacodynamic Analysis Sets (see Section 5.4) will be utilized, if not specified otherwise. Derivation of PD Parameters can be found in Section 6.8.

The handling of ICEs for the change in concentration of PD parameters (NE, CatG, and PR3) will follow the On-IP approach (see Section 2).

# 11.1. Change in Concentration of Biomarkers (NE, CatG, PR3) in Sputum to Week 52

Concentration data of adults from PK/PD substudy, and main study will be pooled together. Data display will be repeated for adolescents.

Baseline and changes from baseline obtained from sputum for NE, CatG, and PR3 will be summarized. Post-baseline parameter values will be natural-log transformed and statistically analyzed similar to the analysis of post-bronchodilator  $FEV_1$  (mL) in Section 8.3.3. In addition, the percentage change from baseline as detailed in Section 6.8 will be summarized.

The observed time to maximum reduction and maximum reduction (see Section 6.8) for NE, CatG, and PR3 will be reported and listed for each participant.

Individual figures of NE, CatG, and PR3 versus actual time will be presented with all participants overlaid on the same plot for each dose level (spaghetti plots). Treatment groups will be differentiated by line patterns.

Arithmetic mean  $\pm$  SD plots versus nominal time will also be presented with all dose levels for brensocatib and placebo overlaid on the same plot. One plot will be produced for each pharmacodynamic sputum parameter.

In addition, mean of %change (+/- SD) values over time will be produced by parameter using scheduled sampling time by dose level overlaid in the same figure. Further, the %change profiles will be produced over time displaying NE, CatG, and PR3 activities side by side in box plots by treatment group.

CONFIDENTIAL Page 84 of 139

# 11.2. Change in Concentration of Biomarkers (NE, CatG, PR3) in Blood to Week 52

The analysis of concentration of biomarkers in sputum in Section 11.1 will be repeated for concentration of biomarkers in blood, except the statistical analysis which will not be produced due to the limited number of participants.

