#### 6.1. General

All summaries will be provided by treatment group, if not stated otherwise (see Section 6.4.2 below). Some presentations will describe specific populations, and this will be evident in each output as necessary.

Descriptive statistics for continuous variables will be calculated at scheduled visits (nominal time points for PK concentration) and will include the number of participants in the treatment group/dose level of the respective Analysis Set (N in column header of the table), the number of non-missing observations (n), arithmetic mean, standard deviation (SD), CV%, median, minimum, and maximum. For NSP concentrations and percent change from baseline in blood and sputum, mean, SD, CV%, median, minimum, maximum will be determined. For brensocatib plasma concentrations and PD results, the geometric mean (GM) with 95% CI and geometric coefficient of variation -percentage (gCV)%, and the number of observations below limit of quantification (BLQ) will also be reported. The GM will be derived by calculating the arithmetic mean of the log-transformed observations and then back-transforming the mean by exponentiation. The gCV% will be calculated as: 100\*sqrt (exp [variance of the log-transformed values] - 1). GM -and gCV% will only be calculated for quantifiable values above 0 (if at least 1 value are less than 0, e.g., for PD parameters, no GM and gCV% will be displayed but left empty). Listings will present the data in its original format.

Categorical variables will be summarized by counts and by percentage of participants in the corresponding categories. The number of participants in the treatment group/dose level of the respective Analysis Set (N in column header of the table) and the number and percentage of non-missing observations in each category will be provided. A category including missing assessments may be added if appropriate. Footnotes will specify the denominator used for the percentages.

In case of mis-randomization to incorrect strata, participants will be analyzed according to the strata into which they were randomized.

Data from unscheduled visits will not be used in summaries, except for the derivation of baseline (see Section 6.4.3).

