#### **Derived activity parameters**

The percentage (%) change from baseline in PD parameters will be calculated as

$$PD_{param1}(\%) = (fold_{change} - 1) * 100$$

While the ratio between post-treatment and baseline results defines the fold change:

$$fold\_change = \frac{post\_treatment\ activity}{pre\_treatment\ activity}.$$

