#### **Pre-treatment / Baseline**

The pre-treatment result is defined as the arithmetic mean of PD parameter results at screening and baseline.

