#### 8.3.3.1. Main Analyses

The Main Estimand of the change from baseline in post-bronchodilator FEV1 (L) at Week 52 is the On-Study Estimand in which all observed data will be included in the analysis (see Section 2). The ITT Analysis Set (see Section 5.2) will be used for this Estimand. The derivation of the endpoint is detailed in Section 6.7.3. Tabulations described below will not be limited to Week 52 but summarize all scheduled time points.

Pre- and post-bronchodilator FEV1 assessments at baseline and Weeks 16, 28, 40, 52 will be summarized by treatment group using descriptive statistics. The summary will include changes from baseline, too.

Change from baseline in post-bronchodilator FEV1 (L) will be analyzed using a linear repeated measures model including treatment group, visit, treatment-by-visit interaction, sputum sample being classified as positive or negative for *Pseudomonas aeruginosa* at Screening Visit, the number of prior PEs [<3 or  $\ge$ 3] in the previous 12 months, stratification region (North America, Europe, Japan, and the Rest of the World), and age group (adult, adolescent) as fixed effects, and baseline value as covariate. The variance-covariance structure will be compound symmetric with the robust sandwich variance estimator (option EMPIRICAL in the PROC-Statement). This analysis will be performed in SAS using MIXED procedure. The OM option will be used to adjust the coefficients for the LSMEANS to reflect the observed data.

If the age group covariate creates estimability issues, it may be removed. If the model still does not converge after removing the age group covariate, other handling including using the parametric covariance estimator instead of the robust sandwich covariance estimator may be applied. When using the parametric covariance estimator, the restricted maximum likelihood (REML) estimator will be applied, with the variance-covariance structure being applied with the following sequence: UN -> TOEPH -> ARH(1) -> CSH. If the model still does not converge, the maximum likelihood estimator will be applied instead of the REML estimator, with the same sequence of the possible variance-covariance structures. The adjustment will be added to the footnote of the corresponding outputs.

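### SAP 11.1 does not state the scale of the baseline covariate in the log-scale sputum biomarker model (read literally, it is unlogged), and the planned arithmetic mean percent change can show a rise within an arm when the typical participant falls

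*SAP*

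**What the plan says.** **Model.** SAP 11.1 states "Post-baseline parameter values will be natural-log transformed and statistically analyzed similar to the analysis of post-bronchodilator" FEV1 and points to SAP 8.3.3. There, change from baseline "will be analyzed using a linear repeated measures model including treatment group, visit, treatment-by-visit interaction", stratification factors and age group "as fixed effects, and baseline value as covariate". On the variance, 8.3.3.1 adds "The variance-covariance structure will be compound symmetric with the robust sandwich variance estimator".

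**Baseline.** For PD parameters SAP 6.8 says "The pre-treatment result is defined as the arithmetic mean of PD parameter results at screening and baseline". This is on the original concentration scale. Protocol 10.4.8 likewise defines the pretreatment NE value as the mean of Screening and Baseline.

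**Not stated.** No passage says whether the PD covariate is logged, or whether the response is ln(post) or a log-scale change. Appendix I has no code for the PD model; its FEV1 code enters baseline as it stands. SAP Table 8 names the variable as a change from baseline summarised by a mean difference. SAP 11.1 mentions no back-transformation to a ratio.

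**Descriptive summaries.** On percent change, SAP 6.8 says "While the ratio between post-treatment and baseline results defines the fold change", and percent change is (fold change - 1) x 100. SAP 6.1 says "For NSP concentrations and percent change from baseline in blood and sputum, mean, SD, CV%, median, minimum, maximum will be determined". SAP 11.1 adds a figure: "mean of %change (+/- SD) values over time will be produced by parameter". It also plans percent-change box plots by treatment group. SAP 6.1 plans a geometric mean with 95% CI for PD results, but leaves it empty when any value is below 0.

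**The concern.** Logging the response acknowledges that these concentrations are right-skewed. For such a marker the raw baseline is a poor linear predictor of ln(post), so adjusting for it recovers only part of the precision that the baseline data could give. Two programmers could also fit different models and both claim to follow the SAP.

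The percent-change summary has a related problem of scale. It cannot go below -100% but has no upper limit, so a few large fold increases can outweigh many real reductions in an arithmetic mean. A baseline below quantification, set to LLOQ/2 under SAP 11, can produce such a value. The geometric mean that would avoid this is left empty for percent change as soon as one participant falls.

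At stake is the clarity of exploratory objective 13. The protocol's study rationale rests on lower sputum protease activity, and a planned figure could appear to contradict the planned model.

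**Working it through.** The documents give no SD, correlation, effect size or precision target for these biomarkers. The PK/PD substudy (about 300 adults) is sized on clinical considerations. There is no stated figure to reproduce, and every SD and correlation below is an assumption shown over a range.

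**1. Precision of the model**

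Setup: log-normal baseline with ln SD s; correlation r between ln(baseline) and ln(post); equal ln SDs before and after; a single-visit ANCOVA standing in for the Week 52 contrast.

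- Correlation of raw with log baseline: k = s / sqrt(exp(s^2) - 1). This gives k = 0.76, 0.51 and 0.27 for s = 1, 1.5 and 2.
- Response ln(post): SE ratio (raw over ln baseline) = sqrt[(1 - r^2 k^2) / (1 - r^2)].
- Response log-change, raw baseline kept: SE ratio = sqrt[((1 - r)^2 (1 - k^2) + 1 - r^2) / (1 - r^2)].

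Example, s = 1.5 and r = 0.6: (1 - 0.36 x 0.265) / 0.64 = 1.41, and the square root is 1.19. The loss of information is 1 - 1/1.41 = 29%.

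| r | ln(post): s = 1 / 1.5 / 2 | log-change: s = 1 / 1.5 / 2 |
|---|---|---|
| 0.4 | 1.04 / 1.07 / 1.08 | 1.09 / 1.15 / 1.18 |
| 0.5 | 1.07 / 1.12 / 1.14 | 1.07 / 1.12 / 1.14 |
| 0.6 | 1.11 / 1.19 / 1.23 | 1.05 / 1.09 / 1.11 |
| 0.7 | 1.18 / 1.31 / 1.37 | 1.04 / 1.06 / 1.08 |

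Simulation with 100 per arm and an ln(post) response gave somewhat smaller ratios for r = 0.5 to 0.7: 1.05 to 1.18 at s = 1, 1.10 to 1.25 at s = 1.5, and 1.11 to 1.32 at s = 2. The mean treatment estimate was about -0.69 to -0.71 throughout, against a true ln(0.5) = -0.693, so there was no bias with either covariate.

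**2. Arithmetic mean percent change**

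For a log-normal fold change with median m and ln SD s, the expected mean percent change is 100 x (m exp(s^2/2) - 1). It is positive when s > sqrt(-2 ln m).

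| True median fall | Sign turns at s | s = 0.5 | 1 | 1.25 | 1.5 | 2 |
|---|---|---|---|---|---|---|
| 30% | 0.85 | -21% | +15% | +53% | +116% | +417% |
| 50% | 1.18 | -43% | -18% | +9% | +54% | +270% |
| 70% | 1.55 | -66% | -50% | -34% | -8% | +122% |

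Example: 0.5 x exp(1.125) = 0.5 x 3.08 = 1.54, so +54%. In simulated arms of 100 with a 50% median fall and s = 1.5, the mean was above zero in 96% of samples and the median in none.

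**The case against.** **The raw covariate is an inference.** SAP 11.1 says the analysis is similar to that of FEV1, not identical. The FEV1 response is a change, and Table 8 calls the PD variable a change, which on the log scale needs ln(baseline). This stands as far as it goes: a reader might infer that the SAP prescribes an unlogged covariate, and it does not. It leaves the scale open, while its wording logs only post-baseline values.

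**The loss may be small.** If the response is log-change, the inflation at correlation 0.7 is 4% to 8% rather than 18% to 37%. If baseline is logged, there is none. This also stands, although below correlation 0.5 the log-change response with a raw covariate does worse. The robust variance estimator protects the validity of inference; it does not restore lost precision.

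**The sign reversal is conditional and confined to one summary.** With an ln SD of 1.5 before and after and correlation 0.6, the fold-change SD is sqrt(2 x 2.25 x 0.4) = 1.34. A 50% median fall then gives 0.5 x exp(0.9) - 1 = +23%. At an ln SD of 1 and the same correlation, the fold-change SD is 0.89 and no reversal occurs. The placebo arm would be inflated too: at s = 1.5 with no change it shows +208%, and 1.54 / 3.08 = 0.5 recovers the true ratio. A reader might infer that the dose-placebo comparison would point the wrong way, and it would not.

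**Other outputs show the direction.** The median, box plots, geometric mean concentrations and log-scale model are all planned. This stands. What remains exposed is the mean percent change within an arm and its mean and SD figure.

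**Conclusion.** The point holds as a gap in specification and an avoidable choice of summary, in an exploratory analysis. Taken literally, SAP 11.1 adjusts a logged response for an unlogged baseline. That costs about 4% to 37% in standard error with an ln(post) response, under ln-baseline SDs of 1 to 2 and correlations of 0.4 to 0.7. These values are assumptions, because the documents give none.

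The mean percent change within an arm turns positive despite a 50% median fall only if the ln fold-change SD exceeds about 1.18. At 0.5 there is no reversal for median falls of 20% or more.

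Two stronger conclusions might be drawn, and the documents support neither. The first is that the treatment estimate is biased: randomisation keeps it unbiased with either covariate. The second is that the trial's efficacy claims are affected: these biomarkers lie outside the 12 hypotheses in SAP 6.3, so no primary or secondary conclusion changes.

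**What to change.** In SAP 11.1:

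- State that the baseline covariate is ln(pre-treatment), keeping pre-treatment as the mean of the screening and baseline results. Redefining it as a geometric mean is unnecessary and would depart from Protocol 10.4.8.
- Name the response as ln(post/pre-treatment). With ln(pre-treatment) in the model, the treatment effect is the same as for ln(post), because the two responses differ only by the covariate itself.
- Report the treatment effects back-transformed as ratios to placebo with 95% CI.

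In SAP 6.1 and 11.1, replace the arithmetic mean and SD of percent change with (geometric mean fold change - 1) x 100 and its 95% CI, in both the tables and the figure. Keep the median and the box plots.

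The cost is SAP wording and small programming changes. No new data, assays or participants are needed.
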